**PILL DIARY PAGE 2 of 3**

**DO NOT THROW AWAY YOUR PILL BOTTLE!  
BRING IT ALONG WITH THIS PILL DIARY TO YOUR NEXT STUDY VISIT.**

DAY	DATE	TIME	COMMENTS	INITIALS
1				
2				
3				
4				
5				
6				
7				
8				
9				
10				
11				
12				
13				
14				
15				
16				
17				
18				
19				

**PILL DIARY PAGE 3 of 3**

**DO NOT THROW AWAY YOUR PILL BOTTLE!  
BRING IT ALONG WITH THIS PILL DIARY TO YOUR NEXT STUDY VISIT.**

20			
21			
22			
23			
24			
25			

I reviewed this Pill Diary with the participant	_____ / ____ / ____ (Reviewer's signature) (Date)
I verify the information on this Pill Diary is correct.	_____ / ____ / ____ (Participant's signature) (Date)

**APPENDIX C: TOBACCO AND ALCOHOL RESOURCES**

## **National and Local Resources to Help with Alcohol Abuse and Alcoholism**

NIAAA's online guide *Treatment for Alcohol Problems: Finding and Getting Help* is written for individuals, and their family and friends, who are looking for options to address alcohol problems. It is intended as a resource to understand what treatment choices are available and what to consider when selecting among them.

<https://pubs.niaaa.nih.gov/publications/treatment/treatment.htm>

## National and local resources to help with quitting smoking

NCI's [Smokefree.gov](http://Smokefree.gov) offers science-driven tools, information, and support that has helped smokers quit. You will find state and national resources, free materials, and quitting advice from NCI.

Smokefree.gov was established by the [Tobacco Control Research Branch](#) of NCI, a component of the National Institutes of Health, in collaboration with the Centers for Disease Control and Prevention and other organizations.

Publications available from the Smokefree.gov Web site include the following:

- [Clearing the Air: Quit Smoking Today](#) for smokers interested in quitting.
- [Clear Horizons](#) for smokers over age 50.
- [Staying Smoke-Free for Good](#) for smokers who have recently quit.
- [Smoke-free](#) for women, including pregnant women.
- [Smoke-free](#) information in Spanish
- [Pathways to Freedom: Winning the Fight Against Tobacco](#) for African American smokers.

NCI's **Smoking Quitline at [name] ([name])** offers a wide range of services, including individualized counseling, printed information, referrals to other resources, and recorded messages. Smoking cessation counselors are available to answer smoking-related questions in English or Spanish, Monday through Friday, 8:00 a.m. to 8:00 p.m., Eastern time. Smoking cessation counselors are also available through [LiveHelp](#), an online instant messaging service. LiveHelp is available Monday through Friday, 8:00 a.m. to 11:00 p.m., Eastern time.

Your state has a toll-free telephone quitline. Call **[name] ([name])** to get one-on-one help with quitting, support and coping strategies, and referrals to resources and local cessation programs. The toll-free number routes callers to state-run quitlines, which provide free cessation assistance and resource information to all tobacco users in the United States. This initiative was created by the [Department of Health and Human Services](#). For more information about quitlines, [speak to an expert](#) on the Smokefree.gov Web site.

10/3/18

**APPENDIX D: TOBACCO AND ALCOHOL QUESTIONNAIRES**

UWI2016-07-01: Phase IIB Randomized, Placebo-Controlled Trial of ACTOplus met® XR in Subjects with Stage I-IV Squamous Cell Carcinoma of the Oral Cavity or Oropharynx Prior to Definitive Treatment	PID#: _____ Date: ____/____/____
--	-------------------------------------

**TOBACCO ASSESSMENT – BASELINE**

**Instructions:**

**When a number is requested in the response, please enter a whole number (i.e. “4”) and not a range or fraction of a number.**

**Section A. Basic Cigarette Use Information**

1. Have you smoked at least 100 cigarettes (5 packs = 100 cigarettes) in your entire life?

- Yes
- No → **Skip to Section B**
- Don't know/Not sure → **Skip to Section B**

2. How old were you when you first smoked a cigarette (even one or two puffs)?

\_\_\_\_\_ Years old

3. How old were you when you first began smoking cigarettes regularly?

- \_\_\_\_\_ Years old
- Check here if you have never smoked cigarettes regularly.

4. How many total years have you smoked (or did you smoke) cigarettes? Do not count any time you may have stayed off cigarettes.

\_\_\_\_\_ Years (If you smoked less than one year, write “1.”)

5. On average when you have smoked, about how many cigarettes do you (or did you) smoke a day? (A pack usually has 20 cigarettes in it).

\_\_\_\_\_ Number of cigarettes per day

6. Do you NOW smoke cigarettes?

- Everyday
- Some days
- Not at all → **Skip to question 8**

UWI2016-07-01: Phase IIB Randomized, Placebo-Controlled Trial of ACTOplus met® XR in Subjects with Stage I-IV Squamous Cell Carcinoma of the Oral Cavity or Oropharynx Prior to Definitive Treatment

PID#: \_\_\_\_\_

Date: \_\_\_/\_\_\_/\_\_\_\_\_

7. How soon after you wake up do you smoke your first cigarette?

- Within 30 minutes  
 After 30 minutes

8. How long has it been since you last smoked a cigarette (even one or two puffs)?

*First check which one of the following choices applies to you. Then, if applicable, write a number on the line for how many days, weeks, months, or years it has been since your last cigarette.*

- I smoked a cigarette today (at least one puff)  
 1-7 days → Number of days since last cigarette \_\_\_\_\_  
 Less than 1 month → Number of weeks since last cigarette \_\_\_\_\_  
 Less than 1 year → Number of months since last cigarette \_\_\_\_\_  
 More than 1 year → Number of years since last cigarette \_\_\_\_\_  
 Don't know/Don't remember

### **Section B. Use of Other Forms of Tobacco**

9. Have you ever used other forms of tobacco, not including cigarettes?

- Yes  
 No → **Skip to Section C**

10. How often do you/did you use other forms of tobacco?

- Every day → Number of times per day \_\_\_\_\_  
 Some days → Number of days \_\_\_\_\_ per  Week  Month  Year

UWI2016-07-01: Phase IIB Randomized, Placebo-Controlled Trial of ACTOplus met® XR in Subjects with Stage I-IV Squamous Cell Carcinoma of the Oral Cavity or Oropharynx Prior to Definitive Treatment	PID#: _____ Date: ____/____/____
--	-------------------------------------

11. Which of the following products have you ever used regularly?

**Check all that apply**

- Cigarettes
- E-cigarettes or other electronic nicotine delivery system
- Traditional cigars, cigarillos or filtered cigars
- Pipes
- Waterpipe
- Hookah
- Clove cigarettes or kreteks
- Bidis
- Smokeless tobacco, like dip, chew, or snuff
- Snus
- Paan with tobacco, gutka, zarda, khaini
- Other, Please specify: \_\_\_\_\_

12. If you do not currently use other forms of tobacco, but did in the past, how long has it been since you last used other forms of tobacco regularly?

- Within the past month (0 to 1 month ago)
- Between 1 and 3 months (1 to 3 months ago)
- Between 3 and 6 months (3 to 6 months ago)
- Between 6 and 12 months (6 to 12 months ago)
- Between 1 and 5 years (1 to 5 years ago)
- Between 5 and 15 years (5 to 15 years ago)
- More than 15 years ago
- Don't know/Not sure
- Never used other forms of tobacco regularly

**Section C. Second-Hand Smoke Exposure**

13. Are you currently living with a smoker?

- Yes
- No

UWI2016-07-01: Phase IIB Randomized, Placebo-Controlled Trial of ACTOplus met® XR in Subjects with Stage I-IV Squamous Cell Carcinoma of the Oral Cavity or Oropharynx Prior to Definitive Treatment	PID#: _____ Date: ____/____/____
--	-------------------------------------

14. In the past 30 days, have you lived in a place where other people smoked cigarettes indoors?

- Yes
- No

15. In the past 30 days, have you worked in a place where other people smoked cigarettes indoors?

- Yes
- No

16. Thinking of all your childhood and adult years, have you ever lived in a place where other people smoked cigarettes indoors?

- Yes → In total, for about how many years? \_\_\_\_\_ If less than 1, write "1."
- No

17. Thinking of all the years you have worked, have you ever worked in a place where other people smoked cigarettes indoors?

- Yes → In total, for about how many years? \_\_\_\_\_ If less than 1, write "1."
- No

**This assessment was completed by:**  Study Team Member  Participant

Completed By: \_\_\_\_\_ Date \_\_\_\_/\_\_\_\_/\_\_\_\_  
*(Signature of person completing)* *(MM/DD/YYYY)*

Completed By: \_\_\_\_\_  
*(Printed name of person completing)*

UWI2016-07-01: Phase IIB Randomized, Placebo-Controlled Trial of ACTOplus met® XR in Subjects with Stage I-IV Squamous Cell Carcinoma of the Oral Cavity or Oropharynx Prior to Definitive Treatment	PID#: _____ Date: ___/___/_____
--	------------------------------------

### ALCOHOL ASSESSMENT – BASELINE

**Instructions:**

**For the following questions about drinking alcoholic beverages, a drink means a 12 oz. beer, a 5 oz. glass of wine, or one and a half ounces of liquor.**

**When a number is requested in the response, please enter a whole number (i.e. “4”) and not a range or fraction of a number.**

1. In your entire life, have you had at least 12 drinks of any kind of alcoholic beverage?

- Yes
- No **(End)**
- Refused **(End)**
- Don't know/Not sure

2. In the past 12 months, on average, how often did you drink any type of alcoholic beverage?

\_\_\_\_\_ (Enter the number of days you drank based on the timeframe checked below. Enter 0 if you never drank and skip to Question 6.)

- Week
- Month
- Year
- Refused
- Don't know/Not sure

3. In the past 12 months, on those days that you drank alcoholic beverages, on average, how many drinks did you have per day?

\_\_\_\_\_ (Enter the average number of drinks per day)

- Refused
- Don't know/Not sure

4. In the past 12 months, on how many days did you have 5 or more drinks of any alcoholic beverage?

\_\_\_\_\_ (Enter the number of days you had 5 or more drinks, or enter 0 if none.)

- Refused
- Don't know/Not sure

UWI2016-07-01: Phase IIB Randomized, Placebo-Controlled Trial of ACTOplus met® XR in Subjects with Stage I-IV Squamous Cell Carcinoma of the Oral Cavity or Oropharynx Prior to Definitive Treatment	PID#: _____ Date: ___/___/_____
--	------------------------------------

5. Was there ever a time or times in your life when you drank 5 or more drinks of any kind of alcoholic beverage almost every day?

- Yes
- No
- Refused
- Don't know/Not sure

6. If you do not currently drink alcoholic beverages, but did in the past, how long has it been since you last drank regularly?

- Within the past month (0 to 1 month ago)
- Between 1 and 3 months (1 to 3 months ago)
- Between 3 and 6 months (3 to 6 months ago)
- Between 6 and 12 months (6 to 12 months ago)
- Between 1 and 5 years (1 to 5 years ago)
- Between 5 and 15 years (5 to 15 years ago)
- More than 15 years ago
- Don't know/Not sure
- Never drank regularly

7. At the heaviest point, either now or in the past, on the days when you drank, about how many drinks did you drink a day on the average?

\_\_\_\_\_ (Enter the number of drinks a day)

- Refused
- Don't know/Not sure

8. How many years have you been drinking (or did drink) regularly?

\_\_\_\_\_ years

- Refused
- Don't know/Not sure

UWI2016-07-01: Phase IIB Randomized, Placebo-Controlled Trial of ACTOplus met® XR in Subjects with Stage I-IV Squamous Cell Carcinoma of the Oral Cavity or Oropharynx Prior to Definitive Treatment	PID#: _____ Date: ___/___/___
--	----------------------------------

9. At what age did you begin drinking regularly?

\_\_\_\_\_ years of age

- Refused  
 Don't know/Not sure

10. What type(s) of alcohol do you drink? (Mark ALL that apply)

- Wine  
 Liquor  
 Beer  
 Wine cooler

**This assessment was completed by:**  Study Team Member  Participant

Completed By: \_\_\_\_\_ Date \_\_\_/\_\_\_/\_\_\_  
(Signature of person completing) (MM/DD/YYYY)

Completed By: \_\_\_\_\_  
(Printed name of person completing)

UWI2016-07-01: Phase IIB Randomized, Placebo-Controlled Trial of ACTOplus met® XR in Subjects with Stage I-IV Squamous Cell Carcinoma of the Oral Cavity or Oropharynx Prior to Definitive Treatment

PID#: \_\_\_\_\_

Date: \_\_\_/\_\_\_/\_\_\_

### TOBACCO ASSESSMENT - FOLLOW-UP

#### Instructions:

When a number is requested in the response, please enter a whole number (i.e. "4") and not a range or fraction of a number.

1. Do you NOW smoke cigarettes?

- Everyday
- Some days
- Not at all → **Skip to Question 3.**
- Never smoked → **Skip to Question 4**

2. On average, when you smoked, about how many cigarettes do you (or did you) smoke a day? (A pack usually has 20 cigarettes in it).

\_\_\_\_\_ Number of cigarettes per day

3. How long has it been since you last smoked a cigarette (even one or two puffs)?

*First check which one of the following choices applies to you. Then, if applicable, write a number on the line for how many days, weeks, months, or years it has been since your last cigarette.*

- I smoked a cigarette today (at least one puff)
- 1-7 days → Number of days since last cigarette \_\_\_\_\_
- Less than 1 month → Number of weeks since last cigarette \_\_\_\_\_
- Less than 1 year → Number of months since last cigarette \_\_\_\_\_
- More than 1 year → Number of years since last cigarette \_\_\_\_\_
- Don't know/Don't remember

4. Since your last visit, have you used other forms of tobacco, not including cigarettes?

- Yes
- No (**End**)

5. How often do you/did you use other forms of tobacco?

- Every day → Number of times per day \_\_\_\_\_
- Some days → Number of days \_\_\_\_\_ per  Week  Month  Year

UWI2016-07-01: Phase IIB Randomized, Placebo-Controlled Trial of ACTOplus met® XR in Subjects with Stage I-IV Squamous Cell Carcinoma of the Oral Cavity or Oropharynx Prior to Definitive Treatment	PID#: _____ Date: ____/____/____
--	-------------------------------------

6. Since your last visit, which of the following products have you used? **Check all that apply**

- Cigarettes
- E-cigarettes or other electronic nicotine delivery system
- Traditional cigars, cigarillos or filtered cigars
- Pipes
- Waterpipe
- Hookah
- Clove cigarettes or kreteks
- Bidis
- Smokeless tobacco, like dip, chew, or snuff
- Snus
- Paan with tobacco, gutka, zarda, khaini
- Other, Specify \_\_\_\_\_

7. If you do not currently use other forms of tobacco, but did in the past, how long has it been since you last used other forms of tobacco regularly?

- Within the past month (0 to 1 month ago)
- Between 1 and 3 months (1 to 3 months ago)
- Between 3 and 6 months (3 to 6 months ago)
- Between 6 and 12 months (6 to 12 months ago)
- Between 1 and 5 years (1 to 5 years ago)
- Between 5 and 15 years (5 to 15 years ago)
- More than 15 years ago
- Don't know/Not sure
- Never used other forms of tobacco regularly

The following instructions pertain to questions 8 - 10. During each of the following time frames, please indicate whether you smoked cigarettes every day, some days, or not at all.

8. During study treatment

- Smoked every day
- Smoked some days
- Did not smoke at all
- Don't know/not sure
- Not applicable

UWI2016-07-01: Phase IIB Randomized, Placebo-Controlled Trial of ACTOplus met® XR in Subjects with Stage I-IV Squamous Cell Carcinoma of the Oral Cavity or Oropharynx Prior to Definitive Treatment	PID#: _____ Date: ___/___/_____
--	------------------------------------

9. After the end of study treatment

- Smoked every day
- Smoked some days
- Did not smoke at all
- Don't know/not sure
- Not applicable (I have not completed the study treatment)

10. Since your last visit to this clinic

- Smoked every day
- Smoked some days
- Did not smoke at all
- Don't know/not sure
- Not applicable (This is my first visit to this clinic)

**This assessment was completed by:**  Study Team Member  Participant

Completed By: \_\_\_\_\_ Date \_\_\_/\_\_\_/\_\_\_\_\_  
*(Signature of person completing)* *(MM/DD/YYYY)*

Completed By: \_\_\_\_\_  
*(Printed name of person completing)*

UWI2016-07-01: Phase IIB Randomized, Placebo-Controlled Trial of ACTOplus met® XR in Subjects with Stage I-IV Squamous Cell Carcinoma of the Oral Cavity or Oropharynx Prior to Definitive Treatment	PID#: _____ Date: ____/____/____
--	-------------------------------------

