#### 2.3.4 Tobacco and Alcohol Use

Tobacco and alcohol use are known risk factors for cancers of the aerodigestive system. In addition, tobacco and alcohol use may adversely affect agent intervention, for example by altering the safety profile or metabolism of a drug. Standardized assessments of tobacco and alcohol use during clinical trials will aid in understanding the potential relationship between the use of these products and clinical endpoints or cancer prevention biomarkers. NCI, DCP is including assessment of tobacco and alcohol use at baseline and end of study visits to determine the potential impact of tobacco and alcohol use on 1) treatment toxicity and symptom burden, and 2) the efficacy of treatment intervention.

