**ALCOHOL ASSESSMENT - FOLLOW-UP**

**Instructions:**

**For the following questions about drinking alcoholic beverages, a drink means a 12 oz. beer, a 5 oz. glass of wine, or one and a half ounces of liquor.**

**When a number is requested in the response, please enter a whole number (i.e. "4") and not a range or fraction of a number.**

1. During the past 30 days, did you drink any alcoholic beverages?

- Yes
- No **(End)**
- Refused **(End)**
- Don't know/Not sure

2. During the past 30 days, how many days per week or per month did you drink any alcoholic beverages, on the average?

\_\_\_\_\_ (Enter number of days you drank based on the timeframe checked below. Enter 0 if you did not drink.)

- Week
- Month
- Refused
- Don't know/Not sure

3. On the days when you drank, on average, about how many drinks did you have?

\_\_\_\_\_ (Enter the average number of drinks you had per day.)

- Refused
- Don't know/Not sure

UWI2016-07-01: Phase IIB Randomized, Placebo-Controlled Trial of ACTOplus met® XR in Subjects with Stage I-IV Squamous Cell Carcinoma of the Oral Cavity or Oropharynx Prior to Definitive Treatment	PID#: _____ Date: ___/___/_____
--	------------------------------------

4. In the past 30 days, on how many days did you have 5 or more drinks per day?  
\_\_\_\_\_ (Enter the number of days you had 5 or more drinks, or enter 0 if none)

Refused  
 Do not know/Not sure

**This assessment was completed by:**  Study Team Member  Participant

Completed By: \_\_\_\_\_ Date \_\_\_/\_\_\_/\_\_\_  
*(Signature of person completing)* *(MM/DD/YYYY)*

Completed By: \_\_\_\_\_  
*(Printed name of person completing)*

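### On the follow-up tobacco form, answering No to question 4 ends the form, so cigarette-only smokers never reach the one direct question on smoking during study treatment

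*Combined protocol and SAP*

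**What the plan says.** Section 2.3.4 gives the reason for collecting tobacco and alcohol data at baseline and end of study: to "determine the potential impact of tobacco and alcohol use on 1) treatment toxicity and symptom burden, and 2) the efficacy of treatment intervention". Sections 7.1 and 7.4.6 place the follow-up form at the end-of-study visit.

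The follow-up tobacco form in Appendix D is a single run of ten questions without sections.

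- Question 1 asks "Do you NOW smoke cigarettes". Its last branch reads "Never smoked → Skip to Question 4".
- Question 2 asks for the number of cigarettes per day.
- Question 3 asks "How long has it been since you last smoked a cigarette (even one or two puffs", to be answered as today, or in days, weeks, months or years.
- Question 4 asks "Since your last visit, have you used other forms of tobacco, not including cigarettes". Yes continues; No is marked as the end of the form.
- Questions 5 to 7 deal with other tobacco products.
- Questions 8 to 10 return to cigarettes under the instruction "During each of the following time frames, please indicate whether you smoked cigarettes every day, some days, or not at all". The first time frame is "8. During study treatment"; the other two are after treatment ended and since the last clinic visit.

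**The concern.** A question about tobacco other than cigarettes decides who is asked about cigarettes. Followed as printed, the form puts the on-treatment smoking item only to people who also use another tobacco product. No reason for that restriction is given, and it runs against the purpose in Section 2.3.4, for which smoking while on study agent is the most relevant exposure.

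The protocol gives its own grounds for wanting this information. Section 2.2.1 links tobacco carcinogens to NFκB activation, and NFκB to cyclin D1-associated proliferation; the primary endpoint is a proliferation marker. With 24 and 12 evaluable participants planned (Section 13.3), the arms could differ by chance in on-treatment smoking, and one would want to be able to describe that. Section 7.5 provides no follow-up after the intervention, so no later visit is scheduled at which the answer could be recovered.

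**Working it through.** The documents state no figure to reproduce here. The check is a trace of the skip pattern, followed by a look at what the earlier questions can replace.

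**Step 1: every path through the follow-up form**

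| Answer to question 1 | Items then asked | No at question 4 | Yes at question 4 |
|---|---|---|---|
| Every day or some days | 2, 3, 4 | form ends | 5 to 10 |
| Not at all | 3, 4 | form ends | 5 to 10 |
| Never smoked | 4 | form ends | 5 to 10 |

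Every path reaches question 4, and no instruction leads from No at question 4 to question 8. The product list in question 6 includes a cigarette box, but it sits behind the same filter.

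**Step 2: is End really the end of the form?** The form has no sections, so there is nothing smaller for it to end. The follow-up alcohol form uses the same mark to stop the whole questionnaire. The baseline tobacco form has the equivalent filter in its Section B, question 9, and there No sends the respondent on to Section C.

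**Step 3: what questions 1 to 3 still tell us.** Let V be the day of the end-of-study visit, 11 to 22 in the standard schedule (up to 26 if surgery is delayed). The final dose is taken the day before (Section 5.2.5), so dosing runs from Day 1 to Day V − 1. A last cigarette d days ago falls on Day V − d.

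- *1 to 7 days ago.* V = 11 gives Days 10 to 4; V = 22 gives Days 21 to 15. All fall within dosing, so some on-treatment smoking is established. How often is not.
- *2 weeks ago (d = 14).* V = 11 gives 11 − 14 = −3, before Day 1. V = 15 gives Day 1. V = 22 gives Day 8. Whether the participant smoked on treatment depends on the visit day and, near Day 15, on rounding to whole weeks.
- *3 weeks ago (d = 21).* V = 22 gives Day 1; any earlier visit gives a date before Day 1.
- *Months or years ago.* Taking a month as at least 28 days, even V = 26 gives 26 − 28 = −2. There was no smoking on treatment, so nothing is lost.
- *Never smoked.* Nothing is lost.
- *Smokes now, every day or some days.* This is close to the scale of question 8, asked about one day after the last dose. It is a fair stand-in unless the habit changed during dosing.

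The information actually lost is on-treatment frequency for people whose habit changed around dosing, and on-treatment status as well for some who answer question 3 in weeks.

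**The case against.** The skip pattern itself is hard to dispute. The case on the other side is that little depends on it, and most of that case stands.

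- Questions 1 to 3 cover much of the ground, as Step 3 shows. A reader might infer that all on-treatment smoking information is lost for these participants. It is not.
- A reader might also infer that the item is missing for most smokers. The documents give no figure for tobacco use of any kind, so only this can be said: it is missing for every smoker who uses no other tobacco.
- Question 9, on smoking after treatment, would have little to capture, because the form is completed about a day after the final dose.
- Tobacco use appears in no objective, endpoint or planned analysis. Section 2.3.4 states the aim in general terms and does not demand an on-agent exposure window.

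A reader may be tempted to extend the point to the follow-up alcohol form, which asks "During the past 30 days, did you drink any alcoholic beverages" although standard dosing lasts 10 to 21 days, so that roughly 30 − 21 = 9 to 30 − 10 = 20 of the recall days precede the first dose. The documents do not make that an error. A fixed 30-day recall is a coherent choice for what Section 2.3.4 calls standardized assessments. Nor is the form presented as a check on the alcohol limits in Section 5.4.2; exclusion 4.2.15 and the pill diary reminder address those. A shorter window would not turn it into one: its question 3 is an average and its question 4 counts only days with 5 or more drinks, whereas the limit for women is passed at more than 3.

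What the objection does not remove is that the form includes a direct question on smoking during treatment and then, without stated reason, withholds it from cigarette-only smokers.

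**Conclusion.** The routing is wrong as printed. Participants who use no other tobacco, including all cigarette-only smokers, are not asked questions 8 to 10, and question 8 is the only direct item on cigarette smoking during study treatment. The loss is limited to direct on-treatment frequency, and in some cases status, for the groups identified above. The number affected could lie anywhere from 0 to the 39 planned participants, because no tobacco-use figures are given.

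It would be a mistake to infer that the efficacy result is at risk. The primary Ki-67 comparison uses none of these data, and Section 13 specifies no tobacco analysis. The defect bears on the descriptive purpose in Section 2.3.4.

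The conclusion assumes that the form is completed as printed and that the database page carries the same skip. If staff ask questions 8 to 10 regardless, the data would be collected unevenly rather than lost.

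**What to change.** At question 4 of the follow-up tobacco form, replace the end mark on No with a skip to question 8. Never-smokers sent there can answer that they did not smoke or that the item does not apply; question 8 already offers both. Moving questions 8 to 10 ahead of question 4 would also work, but the questions and the existing skip references would then need renumbering.

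The cost is one line on the form, the matching change to the electronic page and its specification (Section 12.2 sends such changes to the sponsor's protocol office for approval), and inclusion in the next protocol amendment. It adds three short questions for the participants concerned and no visit or procedure.

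For anyone who has already completed the form as printed, code blank answers to questions 8 to 10 as not asked, not as no smoking. Describe on-treatment smoking from questions 1 to 3 with that limit stated.
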